
**Aim 1. Discover Phase (3 months)** Using iterative and participatory methods, we will work with 10 paraprofessionals who had been trained in telephone-based cognitive behavioral therapy (tCBT) to discover challenges they face in delivery of tCBT, identify areas in the traditional curriculum that supported their skill acquisition, and areas that were missing from the training. Feedback from study team members with expertise in teaching bachelor-level students and other key stakeholders will help inform this process. This information will be used to build the adaptive algorithm in Aim 2. Contribution to the Center: Because the process of educational development includes the identification of competencies that are challenging to learn, data from this phase will be used to inform the Typology of EBPI Targets.

**Aim 2. Design and Build Phase (9 months).** After identifying educational modification targets, and key decisional dilemmas to be built into the program, we will build an Intelligent Tutoring System (ITS) in tCBT via rapid iterative design. The 6 trainees who participated in the *Discover* phase will be actively involved in the *Design/Build* phase, in conjunction with educational experts in tCBT. Contribution to the Center: Data from this phase will be used to inform the Matrix of EBPI Modifications.

[figure not shown]
**Aim 3: Test Phase (18 months).** We will test and compare the addition of an ITS in tCBT to training-as-usual in a small-scale randomized controlled trial. Ten to twelve students will be randomized to the two conditions.

**H1:** The ITS will result in better rating of tCBT usability (AFLA-Q Acceptability, System Usability and User Burden Scales), and student confidence in using tCBT compared to traditional training. **H2:** Students

randomized to the ITS will certify faster (hours in training), and will more competently deliver tCBT elements (number of sessions rated below standard by experts and time to first session rated below standard) than clinicians randomized to traditional training. **H3:** Patients treated by computer-trained students will report better outcomes on functional disability (SDS; Sheehan Disability Scale), and change in depression symptoms over time (PHQ-9 total score) than those treated with traditionally trained students. We will conduct preliminary analysis to determine if change in clinical outcomes is mediated by clinician quality.

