**4. Study Purpose.** Using our Center's *Discover, Design/Build, and Test* (DDBT) framework, we will create—in close collaboration with former paraprofessionals who were trained traditionally in telephone-based CBT (tCBT)—an Intelligent Tutoring System (ITS) for tCBT. We will compare this approach to traditional education plus roleplay training on perceived usability of tCBT post training, clinician time to certification, skill drift over time, and patient-reported outcomes. *Why focus on telephone-based CBT?* Preliminary evidence finds that CBT is an effective treatment for depression in Latino populations. We recently demonstrated that versions of tCBT are not only acceptable, but are effective interventions for rural Latinos suffering from depression. *Why focus on rural Latinos?* Latinos face barriers in the accessibility, availability and provision of mental health services. While they are more likely than the general US population to use primary care settings as their source of behavioral health care, psychotherapy is rarely available to them, particularly in rural communities. Among Mexican Americans, the largest subgroup of Latinos in the country and in our state, only a third with depression receive any care, and only 12% receive care concordant with practice guidelines.

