#### INNOVATION

The main innovation from this R34 is in the use of adaptive training models to build clinical competencies in paraprofessionals working with low-income, rural Latino patients. Our program builds on past efforts to use computerized training in two ways (1) by including the experiences of past trainees in building the curriculum as well as its features (e.g., computerized avatars versus real patient scenarios), and (2) by using game-based algorithms that utilize behavioral psychology principles to enhance educational engagement. We will test whether this program is successful at building a much-needed workforce in a short time period, while building provider effectiveness in the use of tCBT, and thus generate a workforce of paraprofessionals who are competent in tCBT. A challenge in training paraprofessionals is largely in the need for on-going, intensive supervision. We will evaluate whether adaptive training will result in better sustained skill and lower need for intensive supervision. We point out here that the work we are proposing is a novel ITS for training in EBPIs, and is different from the work on Virtual Patients. The use of Virtual Patients (patient simulations using video game technology) has preliminary evidence for effectively training social work students in mental health assessment. Current versions of Virtual Patients use locked-in algorithms to assess—rather than train—specific skills, where all trainees start at the same place in the simulated case interaction, with minimal adaptation. Furthermore, Virtual Patients are only one avenue for training competencies in mental health. An innovation in our study is that, using our DDBT framework, we will create an intelligent tutoring system that is adaptive and includes a variety of competency building exercises that are more than simulated interactions (see Phase 2/Aim 2 below). Additionally, we intend to build an EBPI ITS that is easily deployed with minimal costs. Current market based virtual patient simulations expensive and have limited evidence base.

[figure not shown]

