**Phase 3/Aim 3: Test Phase (18 months)**. We will conduct a pilot study comparing the tCBT training that includes the ITS program (from the *Design/Build* phase) to the traditional training program and its impact on time to learning tCBT and competency delivering tCBT. Latino bachelor-level social work and nursing students from Heritage University will be invited in the Spring quarter of their junior year to apply to participate in our specialized program. We will randomize 10-12 students in years 1 and 2 (two successive cohorts of 5-6 students each) during the study and each will work with five patients using tCBT

**Patient eligibility.** Sixty patient participants will be identified through Yakima Valley Farmworker’s Clinic electronic health record. Participants must be 18 years old or older, suffering from mild to moderate depression with PHQ-9 scores of 10-20. Identified patients will be contacted by a Methods Core research assistant to conduct a preliminary screening for eligibility, provide a brief description of the study and obtain informed consent.

**Paraprofessional Data Collection.** After training, paraprofessionals will be assigned a total of 5 cases each to assess paraprofessional capacity to conduct tCBT. Two types of data will be collected—paraprofessional

assessment of tCBT usability, and ability to learn tCBT and maintain competency. To measure **intervention usability**, paraprofessionals will complete the ALFA-Q Acceptability Scale, the User Burden Scale (UBS) and the System Usability Scale (SUS), which are core measures for this center (see **Methods Core** for description of scales). These scales will be collected through the UWAC data portal after initial training in tCBT after they have seen their 5th patient. **Learnability** of the tCBT will be measured as time to reach competency during training. To measure **sustained competency**, paraprofessionals will collect audio recordings of patient sessions for review by experts. Drs. [name] and [name] will conduct these reviews using the Cognitive Therapy Scales (CTS) adapted to apply to structured, manualized telephone CBT. The CTS utilizes a 7-point rating scale (0 = *poor*, 6 = *excellent*) and has been used to assess the competence of paraprofessional therapists. Sustained competency will be defined by (1) time to first session rated below average and (2) number of sessions rated below average.

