**Data Analysis.** Aim 3 focuses on pilot feasibility data to inform a larger (future) clinical trial comparing ITS-based training in tCBT to training-as-usual (TAU). Thus, analyses do not focus on hypothesis-driven inferential statistics but on descriptive statistics, graphical summaries, and basic effect sizes. H1: Usability. Differences in clinician-reported usability between ITS training and TAU will be plotted using a dotplot and tested using a *t*-test using the ALFA-Q, SUS, and UBS as dependent variables. H2: Fidelity/Competence: A similar strategy (dotplot, *t*-test) will be used with number of hours to reach certification. Number of sessions with CTS scores in competent range will be summarized as proportions, both by clinician and by treatment. Between-group differences will be tested with a 2-sample proportion test. (Future analyses with larger sample size will use a generalized linear mixed model approach to account for the nested data.) H3: Patient-Reported Outcomes. Histograms and kernel density estimates will be plotted by treatment condition to explore differences on depression outcomes (PHQ-9 total score) and overall daily functioning (SDS). Descriptive statistics (*M* and *SD*) will also be examined by clinician and by treatment, using Cohen's *d* as an effect size summary. A *t*-test will be used to examine treatment differences in patient outcomes. Of ultimate interest is whether the modified training protocol (i.e., ITS vs. TAU) has its impact on patient outcomes through enhanced learnability via clinician competence/fidelity. We will use graphical summaries of the data to explore the relationships that are consistent with mediation (e.g., correlation of usability with patient outcomes [b pathway], and treatment differences on patient outcomes with fidelity partialled out [c' pathway']). The primary focus here is whether the data and relationships appear consistent with mediation, as opposed to a formal test, which will be dramatically under-powered.

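### Does the plan need a change because time to first substandard session has no listed output and the competent-range proportion is not tied to its definition?

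*Combined protocol and SAP*

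**What the plan says.** The endpoint appears in three places under three labels.

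- Specific Aims, Aim 3, H2 measures competent delivery by "number of sessions rated below standard by experts and time to first session rated below standard".
- Approach, Paraprofessional Data Collection, gives the formal definition: "Sustained competency will be defined by (1) time to first session rated below average and (2) number of sessions rated below average". The CTS is described there as a 0 to 6 scale adapted to telephone CBT. A source is cited, and no cutoff is given.
- Approach, Data Analysis, H2, plans a dotplot and t-test of hours to certification. For the session ratings it says: "Number of sessions with CTS scores in competent range will be summarized as proportions", by clinician and by treatment, with a two-sample proportion test.

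On the ratings themselves, the plan says that "paraprofessionals will collect audio recordings of patient sessions for review by experts" and that "paraprofessionals will be assigned a total of 5 cases each". It does not say whether every session is rated.

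Two narrative passages touch the same idea. The Study Purpose item under Significance lists "clinician time to certification, skill drift over time, and patient-reported outcomes" among the comparisons. The Innovation section says: "We will evaluate whether adaptive training will result in better sustained skill and lower need for intensive supervision".

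Data Analysis also sets the status of all this: "analyses do not focus on hypothesis-driven inferential statistics but on descriptive statistics, graphical summaries, and basic effect sizes".

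**The concern.** A reader who goes from the definition to the analysis finds two components defined and one analysed. Hours to certification measures learning during training, so it is not an output for sustained competency. Time to the first poor session gets no plot, summary, test or censoring rule. The descriptive aim would explain a missing test, but not a missing description.

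The labels add doubt. *Below standard*, *below average* and *competent range* are never equated, so the reported proportion may or may not be the complement of the failing sessions that H2 counts. A proportion also ignores session order, so it cannot show drift. If only some sessions were rated, the meaning of a first failure would depend on which ones.

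At stake would be one half of the competence endpoint that this pilot is meant to hand on to a larger trial.

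**Working it through.** **Inputs.** 10-12 students, 5 cases each and sixty patients (Approach, Phase 3); 8 sessions per case of 35-40 minutes (Approach, Training program); two expert reviewers (Paraprofessional Data Collection); 10 months of patient recruitment and data collection (Timeline). The plan states no power, alpha or effect size for this endpoint, so there is no such figure to reproduce. The patient count does reproduce at the upper end: 12 × 5 = 60 (10 × 5 = 50).

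**Step 1. Definition against output.**

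| Component | Defined | Listed output |
|---|---|---|
| Number of poor sessions | H2 and Data Collection | Proportion in competent range, by clinician and by treatment |
| Time to first poor session | H2 and Data Collection | None |

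**Step 2. Can the proportion stand in for the time?** No. With k poor sessions among m rated, the first can fall anywhere from 1 to m − k + 1. If all 5 × 8 = 40 sessions are rated and k = 10, the range is 1 to 40 − 10 + 1 = 31. At 20% poor:

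| Rated per case | m | k | Range of first poor session |
|---|---|---|---|
| 1 | 5 | 1 | 1-5 |
| 2 | 10 | 2 | 1-9 |
| 4 | 20 | 4 | 1-17 |
| 8 | 40 | 8 | 1-33 |

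These are logical bounds. They show that the two components differ; they do not show that any conclusion would change.

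**Step 3. Does the proportion cover the count?** On the ordinary reading, yes. It stands under H2, uses the same CTS ratings, and serves a hypothesis about competent delivery measured by failing sessions. If competent range is the complement of failing, the proportion is 1 − k/m, and k follows once m is shown. Ten poor sessions are 25% of 40 but 50% of 20, so dividing by m is a sensible normalisation when students deliver different numbers of sessions. Since the count is itself half of the definition of sustained competency, the Innovation sentence is not left without an output.

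**Step 4. Are the data at risk?** Nothing says that only a subset is rated. The full load is 10 × 40 = 400 sessions × 35 min = 233 h, up to 12 × 40 = 480 sessions × 40 min = 320 h. Assuming one rating per session and an even spread over two reviewers and 10 months, that is 233/20 ≈ 12 to 320/20 = 16 hours per reviewer per month. This is heavy but does not imply a subset. The automatic deletion in Sources of Materials applies to unopened files on a transfer server; the text does not say that this server holds the only copy.

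**Step 5. How much would the missing component show?** Assume independent sessions with poor-rating probability p, and 40 rated per student. The chance of no event is (1 − p)^40.

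| p (assumed) | No event | Expected among 12 students |
|---|---|---|
| 1% | 67% | 8.0 |
| 2% | 45% | 5.3 |
| 5% | 13% | 1.5 |
| 10% | 1.5% | 0.2 |

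At low p, about half or more of the students are censored. At higher p nearly all have an event, but there are only 5 or 6 students per arm if the arms are equal.

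**The case for a change.** The strongest case for acting is that the plan gives each other H2 measure at least a summary and leaves this one out, although both H2 and the formal definition name it. Writing it in would cost one line. The CTS has been adapted, so a cutoff in the cited source may not carry over, and a cutoff left open can be chosen after the scores are seen. Competence also enters the exploratory mediation plots.

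Most of these facts stand. The time component has no listed output, and the complement reading is an inference, though the natural one. A report should state the cutoff it used and when it was set.

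Three parts do not stand. The drift and sustained-skill sentences restate the same omission, so they are not further gaps. Subset rating and lost recordings are conjecture. And an open cutoff in a pilot that makes no confirmatory claim leaves a definition to be supplied; it does not make a stated rule wrong.

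**Conclusion.** The concern is accurate as a note on completeness, but it does not call for a change. One of two named components lacks a listed output, and three labels are used where one would do. Analysts fill both gaps in the ordinary course: they apply one CTS cutoff to the ratings, report the proportion with its count and denominator, and read off the first session below the cutoff for each student, treating those with none as censored at their last rated session. That is description, which is what the plan says it will do.

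No stated result, test or decision depends on the missing summary. The sample size was set mainly on practical grounds, and with 10-12 students the time component could show little about a difference between arms.

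The conclusion rests on three assumptions: competent range means not failing; ratings are kept with their session order; and the sessions rated are enough to make a first failure meaningful. The documents contradict none of these. The 40 sessions per student and the per-session probabilities are assumptions used only to gauge size.

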**Training program in telephone-based CBT (tCBT).** tCBT consists of 8 sessions delivered over 10 to 12 weeks. Each session is designed for delivery in 35 - 40 minutes and includes: structured assessment of depressive symptoms (5 min); review of prior session content (5 min); debriefing previous homework assignment (5-10 min); introduction of new material, including in-session examples and exercises (15-20 min); description of the new homework assignment (5-10 min); and a motivational assessment/enhancement exercise focused on the homework assignment (5 min). The current tCBT training program has four key elements: 1) training program content, designed to target competencies of knowledge and attitude, competence in delivering CBT, and fidelity to the treatment; 2) teaching methods, targeting both the cognitive domain (principles and guidelines needed to deliver EBPI) and the affective domain (attitudes and values related to EBPI); 3) simulated case training to practice skills; and (4) teachers and supervisors to provide on-going skill building with actual patients.

Figure 1. DBBT Model for Research Study.

**Study Overview.** To accomplish the aims of the study, this project will be broken down into 3 phases that are tied to each aim of the study: *the Discover phase*, (Aim 1), *the Design and Build phase* (Aim 2), and *the Test phase* (Aim 3; see Fig. 1. For phases 1 and 2, we will work with 10 paraprofessionals who have been trained in tCBT using the traditional mode described above. For phase 3, we will recruit 2 successive cohorts of 5-6 bachelor students from Heritage University and randomize them to the traditional training model and the new adaptive learning method. The study will be conducted over a 2.5 year period during Y01 through Y03. Steps 1 and 2 will be conducted in the first 9 months of the study and Step 3 in the last 15 months (See timeline).

**Phase 1/Aim 1: Discovery (3 months).** The purpose of this phase is to identify key competencies and decisional dilemmas trainees experience when learning tCBT. Drs. [name] and [name] will be responsible for data collection and synthesis in this phase. As is detailed in the **Methods Core**, *Discover* phase data collection involves the identification of user needs, contextual evaluation, and user testing.

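### Neither sustained-competency measure shows direction of change, so nothing planned separates a student's starting level from the skill drift the trial says it will compare

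*Combined protocol and SAP*

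**What the plan says.** **What is to be compared.** Significance, item 4 (Study Purpose), lists among the comparisons "clinician time to certification, skill drift over time, and patient-reported outcomes". The Innovation section adds: "We will evaluate whether adaptive training will result in better sustained skill and lower need for intensive supervision".

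**How it is measured.** Approach, Phase 3/Aim 3, Paraprofessional Data Collection: "Sustained competency will be defined by (1) time to first session rated below average and (2) number of sessions rated below average". H2 in the Specific Aims uses the same pair under a different label for the cut: "number of sessions rated below standard by experts and time to first session rated below standard". The ratings come from expert review of recorded sessions on the CTS, scored 0 to 6. No numeric cut is given, and no rule says how the two components are combined.

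**How it is analysed.** Approach, Data Analysis, H2: "Number of sessions with CTS scores in competent range will be summarized as proportions, both by clinician and by treatment", followed by a two-sample proportion test. That section names no analysis of time to first low session and no summary over session order.

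**Setting.** After training, "paraprofessionals will be assigned a total of 5 cases each", and tCBT has 8 sessions per case. The training programme also includes "teachers and supervisors to provide on-going skill building with actual patients".

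**The concern.** Drift is a statement about change: is a student's later work better or worse than the earlier work? Time to first low session stops looking once the first lapse has occurred. The count, and the proportion derived from the same ratings, are unchanged if the sessions are shuffled. So neither component, and no planned analysis, shows whether a student improved or deteriorated over the caseload.

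Time to first also depends on where the student starts. If the two arms leave training at different levels, which H2 itself anticipates in favour of the tutoring system, that difference enters the measure alongside any drift. The pilot exists to inform a larger trial through descriptive summaries and effect sizes. As planned, it would pass on no clean estimate of drift, and one component could point the wrong way.

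**Working it through.** The plan gives no figure for this endpoint, so there is nothing to reproduce. The check applies the rule literally, then simulates.

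**Inputs.** Cases per student: 5 (Paraprofessional Data Collection). Sessions per case: 8 (Training program in tCBT). Maximum sessions per student: 5 × 8 = 40. The plan does not state the share rated or the unit of time. I assume that sessions are rated in order and time is counted in sessions. T is the first low session; C is the number of low sessions.

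**Step 1: literal records, no assumed risks (40 sessions, all rated).**

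| Low sessions | T | C | Competent |
|---|---|---|---|
| 1–4 (improves) | 1 | 4 | 36/40 = 90% |
| 37–40 (deteriorates) | 37 | 4 | 36/40 = 90% |
| 1–8 (improves) | 1 | 8 | 32/40 = 80% |
| 1 and 34–40 (deteriorates) | 1 | 8 | 32/40 = 80% |
| 21–40 (deteriorates) | 21 | 20 | 20/40 = 50% |

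- Rows 1 and 2: C ties and T favours the student who deteriorated.
- Rows 3 and 4: opposite courses, identical on both components. The slope of the low-session indicator on session order separates them (−0.024 against +0.018 per session).
- Rows 1 and 5: T favours the deteriorating student (21 against 1) and C favours the improving one (4 against 20). No rule settles the conflict.

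**Step 2: level and drift give the same count.** A constant 15% risk gives an expected 40 × 0.15 = 6 low sessions. A risk rising linearly from 10% to 20% averages 15% and also gives 6. Without drift, mean T is about 1/p: 20 sessions at p = 0.05, 5 at p = 0.20. T therefore moves with level even when nothing drifts.

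**Step 3: simulated trials, five students per arm.** Low ratings are independent, with risk changing linearly from first to last session. All risks are assumptions. T is set to the number of sessions plus 1 if there is no lapse. The contrast is the low-rated share in the late half minus that in the early half. Ranges show repeat runs.

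Mirror-image trajectories (same average risk; the improving arm starts worse):

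| Improving v drifting | Sessions | Drifting arm looks better on mean T | Contrast orders arms correctly |
|---|---|---|---|
| 20%→0% v 0%→20% | 40 | 99% | over 99% |
| 40%→0% v 0%→40% | 10 | 96% | over 99% |
| 15%→5% v 5%→15% | 40 | 85% | 95% |
| 15%→5% v 5%→15% | 10 | 68–69% | 78–79% |

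Common starting risk (share of trials in which each measure orders the arms correctly):

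| Stable v drifting | Sessions | Mean T | Count | Contrast |
|---|---|---|---|---|
| 10% v 10%→40% | 10 | 79–80% | 97% | 84–85% |
| 10% v 10%→40% | 40 | 69–70% | over 99% | 98% |
| 5% v 5%→40% | 10 | 92% | over 99% | 91–92% |
| 10% v 10%→20% | 40 | 58–59% | 93% | 76–77% |

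**Step 4: conflict between components.** For single students over 40 sessions, improver 30%→2% against deteriorator 2%→60%: the improver has the earlier T in 84% of pairs but fewer lapses in 94%. The two components disagree in 79%.

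**The case against.** The strongest reply is that the reversal belongs to a chosen scenario. Mirror-image trajectories make the improving student start worse and force the counts to be equal. The plan points towards similar starts: time to reach competency is measured during training, and cases come afterwards. From a common start, time to first usually points the right way, and the existing count orders the arms at least as well as a late-minus-early contrast. This stands, and it limits the size of the problem. It does not remove it. Equal starts between arms are not guaranteed, H2 predicts a competence difference, and the count detects drift only when starting levels match (Step 2).

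A second reply is that a change score is itself a poor definition of sustained competence. Over 40 sessions, late minus early halves gives 0/20 − 4/20 = −20 points for the student low in sessions 1–4, and 0 for one who never lapsed. Taken alone, it ranks the first above the second. This also stands, so change should be added to the level measure and not replace it.

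Third, this is a descriptive pilot, no test of time to first is specified, and the planned proportion ignores order without reversing it. That is correct. But describing drift for the next trial is exactly what the present measures leave out.

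**Conclusion.** The concern holds in limited form. The plan says it will compare drift in skill, but its two measures and its one analysis of session ratings cannot show direction of change or separate starting level from drift. That follows from the definitions and needs no assumed risks.

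The numerical size does rest on assumptions. Time to first favours the drifting arm in about 69–99% of five-versus-five trials under mirror-image courses, but orders the arms correctly in about 58–92% from a common starting risk. These figures assume independent ratings, linear change, and 10 or 40 sessions rated in order.

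A reader might infer that the rule as a whole scores an improving student below a deteriorating one, or that it carries no information on drift. The documents do not support either. The reversal belongs to time to first alone and needs an improver who starts worse. When the deteriorating student has more lapses, the count favours the improver. Nor does any passage say that low ratings will cluster in the first sessions. The consequence is an incomplete measure to carry into the larger trial, not a wrong confirmatory result.

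**What to change.** In Paraprofessional Data Collection, keep the number (or proportion) of low-rated sessions as the measure of competence level. Add one within-student change per student, for example the slope of CTS score on session order across all rated sessions. State how sessions are ordered when cases overlap, for example by calendar date.

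In Data Analysis under H2, add a plot of CTS score against session order by student and arm. Summarise the per-student slopes descriptively by arm, one value per student, and read them together with the level. Report time to first low session as description only, not as stand-alone evidence of sustained skill.

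The cost is a few sentences, one plot and one summary. No new data, raters or patients are needed, because the plan already collects session recordings and CTS ratings. Per-student slopes will be noisy with 10–12 students and should be presented as such.

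### Skill drift is a named between-arm comparison, but the H2 analysis pools each student's sessions without regard to order and leaves time to first below-average session unanalysed

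*Combined protocol and SAP*

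**What the plan says.** Significance, item 4 (Study Purpose), lists four comparisons between the training approaches. The first is perceived usability; the rest are "clinician time to certification, skill drift over time, and patient-reported outcomes". The Innovation section adds: "We will evaluate whether adaptive training will result in better sustained skill and lower need for intensive supervision".

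Two places turn this into measures. H2 in the Specific Aims gives the competence measures as "number of sessions rated below standard by experts and time to first session rated below standard". Approach, Phase 3/Aim 3, Paraprofessional Data Collection, states: "Sustained competency will be defined by (1) time to first session rated below average and (2) number of sessions rated below average". Session recordings are to be rated on the adapted CTS for this purpose.

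Approach, Data Analysis, H2 then covers two things. Hours to certification get a dotplot and a *t*-test. For sessions with patients: "Number of sessions with CTS scores in competent range will be summarized as proportions, both by clinician and by treatment". The arms are then compared by a test of two proportions. A mixed model is left to larger future studies, and the reason given is nesting, not time.

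**The concern.** Drift concerns change in competence as a student goes on seeing patients. Hours to certification are complete before the assigned cases begin, so they carry no information on it. The session analysis adds up competent sessions within student and within arm, and a total does not depend on the order of its parts. The one defined measure that does depend on order, time to first below-average session, does not appear in the analysis section.

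What is at stake is how a lower proportion in one arm would be read. It could mean that students start lower and hold steady, or that they start well and decay. The second pattern bears directly on the stated question about the need for supervision, and on what the future R01 should measure. The planned output would not separate the two.

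**Working it through.** **The plan's own count.** 12 students × 5 cases = 60 patients, which matches the stated sixty; 10 × 5 = 50 does not. No alpha, power or effect size is given for H2, so there is nothing further to reproduce.

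**Promise against analysis.**

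| Item | Promised or defined in | Data Analysis, H2 |
|---|---|---|
| Hours to certification | H2 | dotplot, *t*-test |
| Number of sessions below standard/average | H2; Paraprofessional Data Collection | covered, as the proportion in the competent range |
| Time to first such session | H2; Paraprofessional Data Collection | nothing |
| Skill drift | Study Purpose | nothing by session order, case or date |

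**Sessions per student.** 5 cases (Paraprofessional Data Collection) × 8 sessions (Training program in tCBT) = 40. This is an upper bound, because the documents do not say how many recordings are rated.

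**Equal totals, linear decline.** Let the chance that session *i* is competent be p(i) = 1 − 0.40(i − 1)/39, for i = 1 to 40.
- Mean over 40 sessions: (1.00 + 0.60)/2 = 0.80, the same as a flat 0.80.
- First 8: 1 − 0.40 × 3.5/39 = 0.964.
- Last 8: 0.60 + 0.40 × 3.5/39 = 0.636.
- Fall: 0.964 − 0.636 = 0.328, or about 33 percentage points, none of it visible in the pooled 0.80.

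**Equal totals, fixed sequences of 40 with 30 competent.**

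| Pattern | Pooled | First half | Second half | First lapse |
|---|---|---|---|---|
| Decliner (30 competent, then 10 not) | 0.75 | 1.00 | 0.50 | session 31 |
| Level (every 4th not competent) | 0.75 | 0.75 | 0.75 | session 4 |
| Improver (10 not, then 30 competent) | 0.75 | 0.50 | 1.00 | session 1 |

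An arm of such decliners against an arm of such level students gives z = 0.00 in the two-sample proportion test, with 5 or 6 students per arm. A simulation of 20,000 trials (assumed: 6 students per arm, 40 independent sessions each, two-sided alpha 0.05) compared competence falling linearly from 0.95 to 0.55 with a flat 0.75. The pooled test rejected in 4.7% of runs, about the nominal rate, although the declining arm's expected proportion goes from 0.853 in the first half to 0.647 in the second.

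**Unequal totals.** An always-competent student scores 40/40 = 1.00 and the decliner above 30/40 = 0.75. These do differ. But the level student in the table also scores 0.75, so the lower figure does not reveal its cause.

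**Time to first lapse.** For the flat 0.80 student, 0.80³ = 0.512 and 0.80⁴ = 0.410, so the median first lapse is session 4. For the student falling from 1.00 to 0.60, the product of p(i) is 0.557 over the first 11 sessions and 0.494 over the first 12, so the median is session 12. In the simulation above the medians were session 3 (level) and session 8 (declining). The measure separates the patterns but scores the decliner better. It also penalises one early slip: a student with 39/40 competent and a single lapse at session 3 looks worse than the decliner whose first lapse is at session 31.

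**Time axis.** A course takes 10 to 12 weeks (Training program in tCBT). Five in sequence need 5 × 10 = 50 to 5 × 12 = 60 weeks. Timeline allows 10 months for patient recruitment and data collection, about 10 × 52/12 = 43 weeks. Cases therefore probably overlap, and case number is not a clean measure of time.

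**The case against.** The strongest defence is that the plan does hold an order-dependent measure. Time to first below-average session is defined twice, and for students who have passed certification it is a defensible measure of failure to maintain competence. This stands in part: a reader might infer that every measure in the protocol is blind to decline, and that is wrong. But the measure has no analysis, and it mixes starting level with decline. The certification threshold is not stated, so equal starting levels cannot be assumed.

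A reader might also infer that a declining and a level student always give the same planned result. They do so only when their competent counts are equal.

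Third, this is a descriptive pilot sized for practical reasons, formal H2 does not use the word drift, and no passage defines drift as change from the first case to the fifth. All of this is correct, and it limits how much weight the gap carries. It does not close the gap. The plan says that it favours description, graphs and simple effect sizes, and a plot over session order is exactly that. H1, hours to certification and H3 all have plots; session competence has none.

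Finally, slopes from 10–12 students will be imprecise. This is true, and it is a reason to present them descriptively.

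**Conclusion.** The point holds. Skill drift is a named comparison, yet the only session-level competence analysis discards session order, and the order-dependent measure that the plan defines is not analysed. With equal totals the pooled proportion can hide a fall of about 33 points (96.4% to 63.6%); with unequal totals it cannot separate decline from constantly lower skill. The 33-point figure is an illustration: it assumes a linear fall and that all 40 sessions are delivered and rated.

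The documents do not support the inference that the trial is unable to answer the drift question. The session ratings already planned could answer it descriptively; the analysis as written simply does not ask it. This is a cheap improvement and does not undermine the trial.

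**What to change.** Add to H2 in Data Analysis, labelled descriptive:

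- (a) a plot of each student's CTS rating against session date or session order, by arm;
- (b) one change value per student (slope over session order, or late minus early sessions), summarised by arm, with the between-arm difference and a 95% CI;
- (c) a descriptive summary of time to first below-average session by arm, using one stated cut-off, since the plan variously says below standard, below average and competent range.

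Do not use case number as the time axis. If only some recordings are rated, spread the rated ones over early, middle and late sessions for every student, and settle this before patient sessions start: under Sources of Materials, the server deletes recordings that nobody opens within a set number of days.

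The cost is a little more analysis work, some constraint on which recordings are rated, and acceptance of a wide interval from 10–12 students.
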